A nationwide, parallel-group randomized controlled superiority trial is conducted comparing an adapted MBSR + SAU (intervention) with SOM + SAU (control). The intervention is an interactive adapted videoconferencing MBSR group-training. The training consists of eight 1,5 hour sessions twice a week during 4 weeks. The sessions will be held via interactive videoconferencing. Participants in the control condition will have the possibility to use a self-help daily mindfulness exercise (30 minutes) on a YouTube channel. In total the participants will receive 24 mindfulness and compassion exercises in 4 weeks. Treatment allocation is a 1:1 ratio. Assessments will be conducted at baseline (T0), mid-treatment (T1), and at 1 (T2), 4 (T3) and 7 (T4) months follow-up. Participants randomized to the SOM + SAU condition will be able to participate in an adapted MBSR intervention after they completed the study (7 months).

Randomization

Random assignment to adapted MBSR + SAU or SOM + SAU is electronically conducted by CastorEDC. Randomization is stratified by setting (3 levels: hospital, nursing home, other), prior mindfulness training (yes/no), and profession (3 levels: physician, nurse, other). Block randomization with predefined blocks are used (2 or 4) in order to ensure balanced groups. Diagnostic research assessors conducting clinical interviews were blinded to the treatment allocation.

Sample size

Based on Lai et al.[1], high post-exposure levels of depression, anxiety, insomnia and distress are expected (in 50-70% of healthcare workers). So far, no data exist on changes of these levels of distress in healthcare workers in the COVID-19 pandemic due to interventions.

Therefore, we aim to detect an effect-size of 0.4 ($\alpha=0.05$; $\beta=0.20$; two-tailed). When using t-tests, a sample size of 200 (100 in each arm) is needed. This will suffice to reveal a clinically relevant difference of 5 points on the PHQ-SADS[8] (scale of sum-score 0-78). To overcome attrition, we will increase the size of our groups with 10%. Thus, a total of 220 participants (110 in each group) will be included in this randomized controlled study.

Framework

Both primary and secondary outcomes will be assessed for superiority of an adapted MBSR + SAU above SOM + SAU.

Statistical interim analyses and stopping guidance

Not applicable

Timing of final analysis

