All outcomes will be analyzed collectively after the T4 measurement and the SCID5 interviews have taken place in the last participants (anticipated being June 2022).

Timing of outcome assessments

At baseline participants complete the questionnaires used for our primary/secondary outcomes. The same questionnaire are send after 1 month (post-intervention), and after 4 and 7 months. To measure possible mediators three questionnaires are used at mid-treatment (2 weeks after start of

the intervention). At 7 months the occurrence of psychopathology is measured by the Structured Clinical Interview for DSM-5 (SCID5).

Section 4: Statistical Principles

Confidence intervals and P values

Level of statistical significance

All applicable statistical tests will be 2-sided and will be performed using a 5% significance level.

Description and rationale for any adjustment for multiplicity

Not applicable

Confidence intervals to be reported

All confidence intervals presented will be 95% and two-sided.

Adherence and protocol deviations

Definition of adherence to the intervention and how this is assessed

Adherence implies that participants attended ≥ 4 sessions in the adapted MBSR + SAU group. The MBSR trainer will keep an attendance register.

Participants in the SOM + SAU group will be asked at timepoint T1 and T2 how often they did a mindfulness exercise in the last two weeks.

Analysis populations

All analyses will be conducted in SPSS version 25 and will be performed as intention-to-treat (ITT). The intention-to-treat population will include all randomized patients, according to the treatment they were randomized to receive. Secondary, per protocol analyses will be conducted.

Section 5: Trial Population

Screening data

Potential participants fill out an online registration form expressing their interest for the study. Next, a screening interview by telephone is planned. Study information will be given and in- and exclusion criteria will be checked during this interview. All screened potential participants and their eligibility will be registered.

Eligibility

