The Trimbos/iMTA questionnaire for Costs associated with Psychiatric illness (TiC-P) [25] will be used to collect information on direct healthcare use and paid and informal work-related productivity losses at 7 months. The EuroQol-5D-3L (EQ-5D) will be used to measure health-related quality of life.

COVID-19 related questions and mindfulness practice questions will be asked.

Analysis methods

Treatment effects at T4

Primary analyses will be performed on the intention-to-treat (ITT) sample. ANCOVA will be used to examine the main effect (PHQ-SADS) of the intervention at T4. Roughly, every month during approximately one year a group will start with the intervention (cohort). Due to the expected differences in these groups, cohort effects will be added. Therefore, a Linear Mixed Effect Model will be used for the analyses. Group (adapted MBSR + SAU / SOM + SAU) will be added as fixed effects, while controlling for baseline levels. A random effect for cohort will be added, and if applicable as a fixed effect. Cohen's *d* effect size will be calculated by dividing the adjusted group difference at T4 by the pooled standard deviation at T0. [26]

Difference in occurrence of psychopathology (present/absent) between adapted MBSR + SAU and SOM + SAU assessed by SCID-5 interview at T4 will be tested with Chi-square test.

Course to treatment effect at T4

The course of treatment effects from baseline to T4 for both primary and secondary outcomes (post-traumatic stress symptoms, insomnia, alcohol use, post-traumatic growth, positive mental health) at

T2, T3, and T4 will be evaluated with Linear Mixed Effects Models. Time, group (adapted MBSR + SAU / SOM + SAU) and their interaction will be added as fixed effects, while controlling for baseline levels. A random effect for participant and cohort (random slope and intercept) will be added. Heterogeneous first-order autoregressive (ARH(1)) covariance structure will be used, which assumes that measurements closer in time are more strongly related to each other. Restricted maximum likelihood will be used as estimation method to handle missing data. Cohen's *d* effects size will be calculated by dividing the adjusted group difference between the pooled means (T2, T3, T4) by the pooled standard deviations at T0.[26]

Moderation of the effect

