Moderation will be examined by adding the potential moderator and its interaction with group to the model. Separate models will be run for each possible moderator. The following possible moderators will be used: gender, age, work setting, profession, prior mindfulness training, adherence, baseline depressive, anxiety and somatic symptoms, and baseline perseverative thinking, mindfulness and self-compassion.

Mediation of the effect

Mediation analysis will be performed on per-protocol sample, using the multiple mediation model by Preacher & Hayes.[27] We will examine whether T0 to T1 change in potential mediators (mindfulness skills, self-compassion, and perseverative negative thinking) mediated T0 to T2 change in depressive, anxiety and somatic symptoms, post-traumatic stress symptoms, insomnia, post-traumatic growth and positive mental health.

Any adjustment for covariates

See above

Methods used for assumptions to be checked for statistical methods

Assumptions of normality will be checked and, in case of lack of normality, bootstrapping will be used to account for this problem.

Any planned sensitivity analyses for each outcome

Sensitivity analyses will be conducted by performing the primary and secondary analyses in the per-protocol (PP) sample. The per-protocol analysis set consists of subjects who have a minimum exposure of 4 MBSR sessions (intervention group (adapted MBSR + SAU)). Further sensitivity analysis will be performed depending on possible patterns in missing values and when relevant disbalance in covariates will be observed.

Any planned subgroup analyses for each outcome

Moderation will be examined by adding the potential moderator and its interaction with group to the model. Separate models will be run for each possible moderator. The following possible moderators

will be used: gender, age, profession, work setting, prior mindfulness training, baseline levels of depressive, anxiety and somatic symptoms.

Missing data

No imputation will be needed for baseline measures, because participants were only randomized if T0 was completed. The questionnaires will be filled in an online platform (CastorEDC), in which it is required to fill in an item before continuing to the next item. Therefore, we expect a low number of missing data.

Additional analysis

None

Harms

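### The mediation analysis relates two changes from T0 and names no baseline covariates, which costs precision on the treatment-to-mediator path and leaves the mediator-to-outcome path resting on one untestable assumption

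*SAP*

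**What the plan says.** SAP Section 6, under Mediation of the effect, sets the method and sample: "Mediation analysis will be performed on per-protocol sample, using the multiple mediation model by Preacher & Hayes". It then fixes the variables. The mediators (mindfulness skills, self-compassion, perseverative thinking) enter as change from T0 to T1: "We will examine whether T0 to T1 change in potential mediators". The outcome side is also a change from T0: these mediators are examined as having "mediated T0 to T2 change in depressive, anxiety and somatic symptoms", and likewise for post-traumatic stress, insomnia, post-traumatic growth and positive mental health. No covariate is named.

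The mixed models for the continuous outcomes in the same section do name one: group, or time and group with their interaction, "will be added as fixed effects, while controlling for baseline levels". The covariate heading that follows the mediation paragraph only points back to the text above it. Under Missing data, the SAP says that T0 had to be complete before randomisation. Under Timing of outcome assessments, the mid-treatment measurement is placed two weeks after the start: "To measure possible mediators three questionnaires are used at mid-treatment".

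**The concern.** Mediators and outcomes are different questionnaires, but both differences subtract a score taken on the same day. If a person's T0 mediator and T0 distress are correlated and both drift back towards the mean, the two changes are correlated even when the mediator does nothing to the outcome. Randomisation protects the treatment-to-mediator path, though less fully in a per-protocol sample. It does not protect the mediator-to-outcome path.

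II.5 is a stated secondary question, tested for several outcomes without multiplicity adjustment, and a positive answer would be read as how the training works. There is also a plain loss of efficiency: a change score without its baseline as covariate wastes information that the trial holds for every participant.

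**Working it through.** **Inputs from the SAP.** Two-sided 5% level (Section 4), 1:1 allocation, and a target effect of 0.4 with 80% power (Section 3). The SAP gives no figure for the mediation analysis, so there is none to reproduce. Its general sample size does reproduce: 2 × (1.960 + 0.842)² / 0.4² = 98.1, so 99 per arm (198 in all) by the normal approximation. The exact t-test gives 99.08, so 100 per arm (200), as stated. I use n = 198.

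**Assumptions, because the SAP gives no correlations.** Equal variances over time, one mediator, no mediator-to-outcome effect, and the correlations stated below. Signs are dropped.

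**Step 1: precision of the treatment-to-mediator path.** With T0-T1 correlation ρ, the residual variance is 2(1 − ρ)σ² for the change score and (1 − ρ²)σ² after baseline adjustment. The ratio is (1 + ρ)/2.

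- ρ = 0.7: 0.85, a cut of 15%.
- ρ = 0.5: 0.75, a cut of 25%.

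**Step 2: mediator-to-outcome path under an autoregressive null.** Let the T0 mediator-outcome correlation be r, mediator stability s_M and outcome stability s_Y. Then the covariance of the two changes is (1 − s_M)(1 − s_Y)r and the variance of the mediator change is 2(1 − s_M). The change-on-change slope is therefore (1 − s_Y)r/2. With s_Y = 0.6 and r = 0.5 it is 0.4 × 0.5 / 2 = 0.10 SD. With the T0 mediator and T0 outcome as covariates it is 0. At r = 0 it is 0 either way.

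**Step 3: what this does to the indirect effect.** Simulated trials (3,000 per row, s_M = 0.7, s_Y = 0.6, r = 0.5), with a Monte Carlo interval for the product of the two paths:

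| Treatment shift in mediator | False indirect effect, change scores | Same, T0 adjusted |
|---|---|---|
| 0 | 1% | under 1% |
| 0.2 SD | 8% | 2% |
| 0.3 SD | 16% | 4% |
| 0.4 SD | 20% | 4% |
| 0.5 SD | 23% | 5% |

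Repeat runs move by about one point (17% at 0.3 SD in another run). At r = 0.3 the change-score figures are 3 to 4% at a shift of 0.2 SD and about 12% at 0.5 SD. With three mediators entered jointly, as the SAP plans, the total indirect effect was false in 23 to 33% of trials at r = 0.5 and 12 to 14% at r = 0.3, against 4 to 5% adjusted.

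**Step 4: the same comparison under a trait-state null.** Let each score be a stable trait plus an occasion-specific state, with T0-to-follow-up correlation 0.6 for both measures and a trait correlation of 0.7. Differencing removes the trait, so the change-on-change slope is half the same-day state correlation. The adjusted slope is not zero, because one T0 score measures the trait imperfectly. At state correlation 0, all cross-measure covariances are 0.6 × 0.7 = 0.42. The adjusted slope b and the T0-outcome coefficient c solve 1.6b + 0.42c = 0.42 and 0.84b + c = 0.6, which gives b = 0.168/1.2472 = 0.135.

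| State correlation | Change-score slope | Adjusted slope |
|---|---|---|
| 0 | 0 | 0.135 |
| 0.1 | 0.05 | 0.153 |
| 0.2 | 0.10 | 0.170 |
| 0.3 | 0.15 | 0.187 |
| 0.5 | 0.25 | 0.222 |

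At state correlation 0 and a mediator shift of 0.3 to 0.5 SD, false indirect effects stay near or below 5% with change scores but reach about 32 to 48% with adjustment. At state correlation 0.5 the order reverses.

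**The case against.** The strongest objection is that the autoregressive null favours baseline adjustment by construction. Step 4 bears this out. Mindfulness, self-compassion and perseverative thinking are plausibly trait-like, and where stable traits carry the correlation, differencing removes the confounding that adjustment leaves in. Choosing between the two for an unrandomised path is a choice between assumptions, and nothing in the SAP decides it. This stands, and it rules out simply replacing the planned analysis.

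It also stands that a spurious mediator-to-outcome slope is not a spurious answer to II.5. The indirect effect also needs a treatment effect on the mediator. The 23% belongs to a shift of 0.5 SD, which exceeds the trial's own target ("we aim to detect an effect-size of 0.4") and would have to appear two weeks into treatment against an active mindfulness control. The main simulations use one mediator and 198 participants, not three mediators in the per-protocol sample.

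On wording, the SAP does not describe the changes as raw and does not exclude covariates. A reader might infer a deliberate decision against baseline adjustment. The document supports only silence, with a simple difference as the plain reading of change.

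None of this touches Step 1. The precision gain on the treatment-to-mediator path does not depend on which null is true.

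**Conclusion.** The point holds in two parts. First, the treatment-to-mediator path gives up precision that T0 data already in hand would supply: 15 to 25% of its variance at an assumed T0-T1 correlation of 0.7 to 0.5. Second, the change-on-change mediator-to-outcome path can suggest mediation where there is none. Under the autoregressive null with T0 correlation 0.5, about 17 to 23% of trials show a false indirect effect when treatment shifts the mediator by 0.3 to 0.5 SD, with little or no inflation when it does not.

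A reader might go further and infer that the change-score model is simply wrong and the adjusted model right, or that II.5 will come out positive whatever the truth. The SAP supports neither: it gives no correlations or stabilities, and under correlated stable traits with weakly correlated states the adjusted model is the worse one. The defect is reliance on a single specification with no stated treatment of baseline. This is a secondary, exploratory question.

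**What to change.** Amend the mediation paragraph as follows.

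1. In the treatment-to-mediator equations, include the T0 mediators and the T0 outcome as covariates. With those terms in, the treatment coefficient is the same whether the response is the T1 score or the change.
2. For the mediator-to-outcome path, report two models: T1 mediators and T2 outcome with the T0 mediators and T0 outcome as covariates, and the planned change-score model. Give a bootstrap interval for the indirect effect from each.
3. Claim mediation for II.5 only if both agree, and label it exploratory. Agreement is not proof: in Step 4 both slopes are non-zero once states are correlated.

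The cost is SAP wording, four more covariates per adjusted equation (three mediators and the outcome at T0), one more model per outcome, and a more conservative claim. No new data are needed.

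### The only sensitivity analysis fixed in advance drops MBSR participants with fewer than 4 sessions but applies no rule to SOM, so its contrast is no longer protected by randomisation and can be biased in either direction

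*SAP*

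**What the plan says.** The main analysis set is clear. Section 6, *Treatment effects at T4*, states: "Primary analyses will be performed on the intention-to-treat (ITT) sample". Section 4, *Analysis populations*, makes PP analyses secondary.

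Section 6, *Any planned sensitivity analyses for each outcome*, then says: "Sensitivity analyses will be conducted by performing the primary and secondary analyses in the per-protocol (PP) sample". The set is defined in the next sentence: "The per-protocol analysis set consists of subjects who have a minimum exposure of 4 MBSR sessions (intervention group (adapted MBSR + SAU". Anything further is left open: "Further sensitivity analysis will be performed depending on possible patterns in missing values and when relevant disbalance in covariates will be observed".

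Section 4, *Adherence and protocol deviations*, sets the same cut of at least 4 "sessions in the adapted MBSR + SAU group. The MBSR trainer will keep an attendance register". For SOM it sets no cut; participants "will be asked at timepoint T1 and T2 how often they did a mindfulness exercise in the last two weeks". Section 3, *Trial design*, gives the length of the course: "The training consists of eight 1,5 hour sessions twice a week during 4 weeks". The PP rule therefore asks for half of it.

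The point concerns the treatment-effect analyses: PHQ-SADS at T4, SCID-5, and the course outcomes. It does not concern the moderator analyses or the mediation analysis.

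**The concern.** Attendance is observed after randomisation. People who stop a group course early may differ in prognosis from those who stay. The PP rule removes them from MBSR, while the SOM participants who would have behaved the same way remain. The two groups compared are then no longer alike at the start, and adjustment for the baseline score removes only the part of the difference that the baseline score carries.

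This is the only sensitivity analysis that the plan fixes. A PP estimate larger than the ITT estimate could be taken to confirm the primary result, or to show what MBSR does when it is followed. Under this rule it would be valid evidence for neither.

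**Working it through.** **Inputs from the SAP.** Target effect 0.4 SD, two-sided alpha 0.05, power 0.80, 100 per arm before the attrition allowance, and a relevant difference of 5 PHQ-SADS points (Section 3, *Sample size*). The implied SD is 5/0.4 = 12.5 points.

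**The plan's own figure.** The exact two-sample t-test solution is 99.08 per arm, so 100 per arm and 200 in total. The stated sample size reproduces and is not in dispute.

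**Assumed inputs.** The SAP gives neither of these:
- s, the share of MBSR participants below 4 sessions: 10-35%.
- g, the baseline-adjusted prognostic gap between non-attenders and attenders: 0.2-0.6 SD, non-attenders worse.
- For standard errors: baseline-outcome correlation 0.6, so residual SD √(1 − 0.36) = 0.8, and complete data at T4.

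**Bias with no true effect.** Let the attenders' mean be m (higher is worse). The MBSR PP mean is m. The SOM mean is (1 − s)m + s(m + g) = m + sg. The apparent MBSR benefit is therefore s × g.

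**Rejection rate.** For s = 0.25 and g = 0.3, SE = 0.8 × √(1/75 + 1/100) = 0.122. The bias is 0.075/0.122 = 0.61 SE, which gives two-sided rejection of about 9.4%. Simulated figures (4,000 runs per cell) are beside it:

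| s | g | Bias, SD | Bias, points | Simulated rejection |
|---|---|---|---|---|
| 10% | 0.2 | 0.02 | 0.25 | 4.8-5.6% |
| 25% | 0.3 | 0.075 | 0.94 | 8.8-9.5% |
| 35% | 0.6 | 0.21 | 2.6 | 39% |

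A range in the last column shows separate simulation runs. The middle row is 0.075/0.4 = 19% of the target effect. A different selection model, with 110 per arm, 70-90% attending, and a correlation of 0.2-0.5 between attendance propensity and outcome, gave spurious effects of 0.04-0.25 SD and rejection of 6-40%.

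**With a true effect of 0.40 SD in attenders and none in others (s = 0.25, g = 0.3).**
- ITT: 0.75 × 0.40 = 0.30.
- PP: 0.40 + 0.075 = 0.475.
- Complier estimate: 0.30/0.75 = 0.40.

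**When the complier assumptions fail.**
- SOM is an active comparator. Suppose it gives 0.2 SD to those who would not attend MBSR. ITT is 0.75 × 0.40 − 0.25 × 0.2 = 0.25, and the complier estimate is 0.25/0.75 = 0.33. PP is 0.475 − 0.05 = 0.425. Here PP lies nearer to 0.40.
- Suppose instead that attending fewer than 4 sessions gives 0.2 SD. The complier estimate is (0.30 + 0.05)/0.75 = 0.47.

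**Precision at s = 0.25.** Complier SE ≈ 0.8 × √(2/100)/0.75 = 0.15, against 0.12 for PP.

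**The case against.** The plan already ranks PP below ITT and nowhere says that PP will confirm the primary result. The size rests wholly on assumed inputs, the mildest setting shows almost no inflation, and the sign can reverse. Using SOM is optional (Section 3, *Trial design*), so non-use is not a departure from that assignment, and a one-arm rule has some logic. All of this stands, and it limits the weight of the point. It does not make the contrast a randomised one.

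A reader might infer from the definition that the PP set holds no SOM participants, so that no comparison exists. That reading is strained: the parenthesis ties the 4-session rule to the intervention arm, and a re-run of between-group analyses needs both arms. The fair criticism is that the SOM comparator is not stated.

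A reader might also infer that a complier analysis should simply replace PP. It rests on two untestable assumptions, and the figures above show that it can be further from the truth than PP when one fails. It also largely rescales ITT: in simulation the two significance decisions agreed in 98-100% of trials. It answers a different question and does not fill the place of a robustness check.

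A matching SOM practice threshold removes the bias only in the best case, where both rules select on the same trait to the same degree. MBSR attendance comes from a trainer's register. SOM practice is self-reported at T1 and T2 and would be missing for those who stop responding.

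**Conclusion.** The point holds, with limits. The one sensitivity analysis fixed in advance selects after randomisation in one arm only, so its contrast can be biased. The illustrative size is 0.02-0.21 SD (0.25-2.6 points at the implied SD) over 10-35% non-attendance and a 0.2-0.6 SD residual gap.

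Two stronger conclusions are tempting and unsupported. One is that the PP result will favour MBSR: it does so only if non-attenders have the worse prognosis, on which the SAP has no data. The other is that the trial's main conclusion is compromised: the ITT primary estimate, its test and its interval are untouched.

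**What to change.** 1. In Section 6, state that the PP comparator is all randomised SOM participants. Label every PP result descriptive, including those for the course outcomes, and say that PP will not be used to support or confirm the primary conclusion.

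2. For the effect of attending, add a supplementary complier average causal effect analysis of PHQ-SADS at T4 in all randomised participants. Use two-stage least squares with randomised arm as the instrument for attending at least 4 sessions. SOM attendance is 0, because SOM participants have access to MBSR only after the 7-month study period. Keep the baseline and cohort adjustment of the primary model, with cohort as a fixed effect, which Section 6 already allows. Give a risk-difference version for SCID-5.

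3. State both exclusion assumptions: attending fewer than 4 sessions has no effect, and assignment to SOM rather than MBSR does not change outcomes in those who would not attend MBSR. Vary each, for example from 0 to 0.2 SD, and report the range.

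The cost is SAP wording and a small set of extra models; attendance is already registered. The downside is a wider interval (SE about 0.15 against 0.12 SD at 25% non-attendance) and assumptions that cannot be tested. When neither assignment nor attendance has any effect, the complier test keeps the validity of the ITT test, which the PP re-run does not. It should not be presented as a robustness check of the ITT result.
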